#### ***4.2.3 Secondary outcome assessment***

The secondary outcome of this study is in-hospital mortality, survival analysis, including Kaplan-Meier analysis and log-rank testing, was used to evaluate the association between IAPI and various patient characteristics. Generalized linear mixed-effects regression analysis with a logit link function and a random effect for country was used to account for possible confounding factors. Odds ratios and 95% confidence intervals were used to present the results. We assumed that the occurrence of in-hospital mortality would be rare, ensuring that odds ratio estimates derived from a case-control design could serve as reliable estimators of relative risk for calculating the IAPI mortality attributable fraction. The following approach was used for attributable fraction calculation for each admission type: the inverted probability weights (IPW) for each patient were calculated, representing the cumulative risk of the patient acquiring IAPI during hospitalization, under a multivariable logistic regression analysis including baseline age, Charlson Comorbidity Index, surgical complications, and a time-dependent variable for the occurrence of clinically relevant events. We estimated the association between IAPI occurrence on hospital mortality post operation three months through a mixed logistic regression model weighted by IPW. The delta method was employed to compute the 95% CIs for both the odds ratio and attributable mortality.

We also assessed the incidence and attributable mortality of surgical complications in patients during the same hospitalization by . Additionally, we evaluated the duration of hospital stay and associated costs incurred by patients within this hospitalization period.

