### **Participants and setting:**

All patients who underwent surgery procedure from operating room of more than 5 tertiary hospitals in China.

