### ***2.3 Setting***

The patients will be recruited from the operating rooms of nine tertiary hospitals in China: Affiliated Hospital of Guangdong Medical University (Guangdong), First Affiliated Hospital of Sun Yat-sen University (Guangdong), Foshan First People's Hospital (Guangdong), First Affiliated Hospital of Zhengzhou University (Henan), and The First Affiliated Hospital of Nanchang University (Jiangxi).

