### 3. Data Collection

#### 3.1 Data sources and study setting

The patients will be enrolled from the operating room of nine China tertiary hospitals: Affiliated Hospital of Guangdong Medical University (Guangdong), First Affiliated Hospital of Sun Yat-sen University (Guangdong), Foshan First People's Hospital (Guangdong), First Affiliated Hospital of Zhengzhou University (Henan), The First Affiliated Hospital of Nanchang University (Jiangxi).

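### The mortality analysis adjusts for country, which has one level in this all-China study; hospital is in no stated model, and complications enter the IAPI weights with no timing rule

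*Combined protocol and SAP*

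**What the plan says.** Section 4.2.3 describes two regression models and one set of weights.

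- **Mixed model:** "Generalized linear mixed-effects regression analysis with a logit link function and a random effect for country was used to account for possible confounding factors". The sentence names no outcome. The section opens with in-hospital mortality, so mortality is the natural reading.
- **Weighted model:** the effect of IAPI is estimated "on hospital mortality post operation three months through a mixed logistic regression model weighted by IPW". No grouping factor is given for this mixed model.
- **Weights:** these are described as "representing the cumulative risk of the patient acquiring IAPI during hospitalization", estimated "under a multivariable logistic regression analysis including baseline age, Charlson Comorbidity Index", then surgical complications, "and a time-dependent variable for the occurrence of clinically relevant events". That last variable is not defined anywhere.

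On sites, the abstract refers to the "operating room of more than 5 tertiary hospitals in China". Section 2.3 says "The patients will be recruited from the operating rooms of nine tertiary hospitals in China", and section 3.1 says "The patients will be enrolled from the operating room of nine China tertiary hospitals". Both sections then name only five hospitals, all in China.

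On complications, the abstract lists them as a secondary outcome. Section 2.5.2 and footnote 2 of Table 2 cover the whole hospital stay. Table 2 schedules them at the same follow-up visits as IAPI, from 0.5 hours to 3 months, with no baseline entry.

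**The concern.** A random effect for a factor with one level cannot be told apart from the intercept. The plan relies on this term to deal with confounding, and it deals with none. In a multicentre cohort the obvious shared influence on both IAPI and death is the hospital: case mix, positioning practice, skin inspection and postoperative care. Sections 4.2 to 4.2.4 contain no hospital, centre or site term. An analyst who follows the text leaves any between-hospital difference in the IAPI odds ratio and in the attributable mortality derived from it.

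The second issue is timing. A covariate in a weight model should come before the exposure. A complication that precedes IAPI may be a confounder and belongs there. A complication that results from IAPI lies on the path to death, and weighting on it removes that part of the effect. The plan does not say which complications count. It also does not settle when IAPI occurs: section 2.5.1 attributes the injury to forces during surgery, while section 4.2.3 speaks of acquiring it over the hospital stay.

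**Working it through.** **1. Levels of the random effect.** Abstract, section 2.3 and section 3.1: all sites in China, so country has 1 level. Hospitals: nine stated, five named, more than five in the abstract. As a check, a simulated cohort of 5144 patients in one group (59 deaths) gave a minus log-likelihood of 322.270 at random-effect SD 0, 322.339 at 0.05, 322.500 at 0.1 and 323.186 at 0.3. The fit is best at SD 0. The log odds ratio was -0.0373 at every SD and in plain logistic regression.

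**2. Numbers available.** The plan gives no figure for this analysis, so I use its sample size (section 4.1). The plan's figures reproduce: 4115 / 0.8 = 5144; 5144 x 1.10 = 5658. IAPI incidence is 13.9%. Mortality is not given; I assume 1.2%, with a range of 0.5% to 3%.
- IAPI cases: 5144 x 0.139 = 715, or 79 per hospital with nine equal hospitals and 143 with five.
- Deaths: 5144 x 0.012 = 62 to 5658 x 0.012 = 68, so about 7 (62/9) to 14 (68/5) per hospital. Over the range: 5144 x 0.005 = 26 to 5658 x 0.03 = 170.

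**3. Sampling error.** With odds ratio 1, deaths with IAPI are 62 x 0.139 = 8.6, leaving 53.4 deaths without IAPI, 706.4 survivors with it and 4375.6 without. SE of the log odds ratio = sqrt(1/8.6 + 1/53.4 + 1/706.4 + 1/4375.6) = 0.37. A 95% interval is the estimate multiplied or divided by exp(1.96 x 0.37), about 2.1.

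**4. Omitting hospital (illustration).** Assumed: 5 or 9 equal hospitals, true odds ratio 1, hospital IAPI level SD x z, hospital death level SD x (rho x z + sqrt(1 - rho^2) x w), with z and w standard normal, logit scale, intercepts set to 13.9% and 1.2%, 3000 draws per cell. Median odds ratio at SD 0.3 / 0.5 / 0.7:

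| rho | 5 hospitals | 9 hospitals |
|---|---|---|
| 0.5 | 1.028 / 1.071 / 1.131 | 1.035 / 1.094 / 1.173 |
| 0.3 | 1.017 / 1.039 / 1.073 | 1.021 / 1.055 / 1.094 |
| -0.3 | 0.984 / 0.957 / 0.918 | 0.979 / 0.946 / 0.902 |
| -0.5 | 0.972 / 0.926 / 0.862 | 0.966 / 0.902 / 0.831 |

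At rho 0 the medians are 0.995 to 1.000. Single sets of hospitals vary more: at SD 0.7 and rho 0.3 to 0.5, about 3% to 8% of sets exceed 1.5. Against the sampling SE, ln(1.02)/0.37 = 0.05 and ln(1.17)/0.37 = 0.42.

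**5. Complications that follow IAPI (illustration).** Assumed: complications in 10% to 20% of patients without IAPI, odds ratio of death with a complication 3 to 10, direct IAPI odds ratio 1.5, mortality 1.2%. RR is the factor by which IAPI multiplies the complication risk. Weighting on complications sets both arms to the pooled complication rate. Share lost = 1 - ln(weighted OR) / ln(total OR).

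One case (15%, odds ratio 5, RR 1.5): risk of death without IAPI is 0.687% without and 3.344% with a complication; with IAPI it is 1.027% and 4.933%.
- Total effect: 0.775 x 1.027 + 0.225 x 4.933 = 1.91% against 0.85 x 0.687 + 0.15 x 3.344 = 1.09%, odds ratio 1.77.
- Pooled complication rate: 0.139 x 0.225 + 0.861 x 0.15 = 0.1604. The weighted risks are 1.65% and 1.11%, odds ratio 1.49.
- Share lost: 1 - ln(1.494)/ln(1.770) = 0.30.

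Over the full grid the share lost is 0 at RR 1, 4% to 14% at RR 1.1, 7% to 23% at 1.2, 16% to 41% at 1.5 and 27% to 56% at 2.

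**The case against.** The best defence of the first part is that the covariate list is introduced as a partial one, so hospital is unstated rather than ruled out, and the weighted model may have been meant to group by hospital. That is possible, but the only grouping factor written down is country, and it is inert whichever outcome the sentence refers to.

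On size, the defence is stronger. The typical distortion in step 4 is under half a standard error, all inputs except 13.9% are assumed, and the analysis is secondary to the prediction model. A reader might infer that the IAPI odds ratio is biased upward, or that it would reach 1.5. The documents do not support that: they give no hospital-level rates, the sign depends on an unknown correlation, and values above 1.5 are the exception in step 4, although they do not need perfect correlation.

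On the second part, a reader might infer that the weights certainly remove part of the IAPI effect. That needs three things the documents do not establish: that complications after IAPI are used, that IAPI raises complications, and that the undefined time-dependent variable is not itself the timing rule. If all the complications used precede IAPI, nothing is lost. What stands is that no ordering rule is written. The word baseline before age cannot supply one for complications, which have no baseline entry in Table 2.

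It is also fair to say that the choice between a hospital random intercept, fixed effects and stratification is open with five to nine hospitals.

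**Conclusion.** The first part holds with high confidence: the country term has one level and adjusts for nothing, hospital appears in no stated model, and the weighted mixed model lacks a grouping factor. This follows from the text alone and needs no assumption.

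The second part holds with medium confidence and only conditionally: the plan permits complications that follow IAPI to enter the weights, and whether they would do so depends on how IAPI is dated and on a variable that is not defined.

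The documents do not determine the size or direction of either effect, and steps 4 and 5 only show what is possible under assumed inputs. Only the secondary attributable-mortality analysis is affected. The prediction model and its sample size are not. The correction should be made because it is cheap and because a grouping factor or timing rule chosen after the mortality data are seen would be open to selection.

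**What to change.** 1. In section 4.2.3, replace country with hospital, and name the outcome of that model.
2. Name hospital as the grouping factor of the weighted model: a random intercept, or fixed effects or stratification given the small number of hospitals. Include hospital in the weight model.
3. Reconcile the hospital count across the abstract, section 2.3 and section 3.1, since it sets the number of clusters.
4. State whether IAPI is dated to surgery or to its first recording, restrict the weight covariates to those fixed or recorded before that time, and define the time-dependent variable.

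Items 1 to 3 are mainly wording. Item 4 needs dates or visit labels for IAPI and complications; Table 2 already schedules both by visit. The statistical cost is more parameters with few deaths (about 7 to 14 per hospital at the assumed 1.2%) and an imprecise variance from five to nine hospitals. Splitting by admission type, as the section plans, makes the data sparser still.

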### **Design:**

A prospective, multicenter, cohort study.

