## **2. Methods**

### ***2.1 Study Design***

The proposed study design is a prospective, multicenter, cohort study, which aims to calculate the risk factors that influence the incidence of IAPI. This design allows researchers to observe the natural history of IAPI, and to identify potential risk factors and interventions that may affect the incidence of IAPI.

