## ***2.4 Participants and Eligibility criteria***

Participants who meet the inclusion criteria: all patients who underwent surgery procedure at the participating setting after the study registration.

Exclusion criteria: Patients who have already been diagnosed with pressure injury (stage II and above) before undergoing surgery procedure. Patients/relatives/guardians understand the refusal of data to be used for clinically relevant research. Investigators believe that certain patient conditions may affect the efficacy and safety assessment of this study.

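### The IAPI attributable fraction uses the odds ratio as a relative risk, citing a case-control design the study does not have; the cohort makes this approximation unnecessary

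*Combined protocol and SAP*

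**What the plan says.** Section 4.2.3 (Secondary outcome assessment) rests the attributable fraction on two premises. The first is rarity: "We assumed that the occurrence of in-hospital mortality would be rare". The second is the design: it holds that "odds ratio estimates derived from a case-control design could serve as reliable estimators of relative risk". The association between IAPI and death is to be estimated "through a mixed logistic regression model weighted by IPW", so the effect measure is an odds ratio. The calculation is stratified: "The following approach was used for attributable fraction calculation for each admission type". Confidence intervals come from the delta method.

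The rest of the document describes a different design. The abstract has "A prospective, multicenter, cohort study", and Section 2.1 says "The proposed study design is a prospective, multicenter, cohort study". Section 2.4 takes in "all patients who underwent surgery procedure at the participating setting after the study registration", subject to its exclusions. Section 3.3 and Table 2 collect death at every follow-up contact from 0.5 hours to 3 months.

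No case-control or nested sampling is described anywhere. The document also gives no expected mortality, no threshold for calling death rare, no check of that assumption, no definition of the admission types, and no statement of whether the fraction is among the exposed or in the population.

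**The concern.** A case-control sample fixes the ratio of cases to controls, so absolute risks cannot be read from it without outside information. The odds ratio is then used because the relative risk is not available. A cohort has no such limit: the risk of death with and without IAPI can be estimated, weighted and compared directly. Section 4.2.3 therefore justifies an approximation by a design the study does not have, and makes it depend on a rarity assumption that the plan neither quantifies nor tests.

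Because the fraction is calculated per admission type, rarity has to hold in every stratum and not only overall. Where it fails and IAPI is associated with higher mortality, the share of deaths ascribed to IAPI is overstated. The overstatement grows with baseline risk, so two admission types with the same true relative risk would show different attributable fractions.

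**Working it through.** **Plan's own figure.** There is none to reproduce. The document states no odds ratio, relative risk, mortality rate or attributable fraction. The only input taken from it is the 13.9% IAPI incidence in Section 4.1, used in step 4. All other values are assumptions.

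**1. Formulas.** Let p0 and p1 be the risks of death without and with IAPI.

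- RR = p1/p0, and OR = [p1/(1 − p1)] / [p0/(1 − p0)].
- Fraction among the exposed from the relative risk: 1 − 1/RR = (p1 − p0)/p1.
- The same fraction with the odds ratio put in: 1 − 1/OR = (p1 − p0)/[p1(1 − p0)].
- Ratio of the second to the first: 1/(1 − p0). For RR above 1 the relative overstatement is p0/(1 − p0), whatever the size of the effect.

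**2. One case in full (assumed OR 3, p0 10%).** p1 = 3 × 0.10/(1 − 0.10 + 3 × 0.10) = 0.30/1.20 = 0.25, so RR = 2.5. The risk-based fraction is 1 − 1/2.5 = 60.0%. The odds-ratio version is 1 − 1/3 = 66.7%. The ratio 66.7/60.0 = 1.11 = 1/0.90, as the identity requires.

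**3. Range of assumed baseline risks.** Risk-based fraction = (1 − p0)(1 − 1/OR).

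| Assumed p0 | Relative overstatement p0/(1 − p0) | OR 3: odds-ratio version 66.7%, risk-based | OR 2: odds-ratio version 50.0%, risk-based |
|---|---|---|---|
| 1% | 1.0% | 66.0% | 49.5% |
| 2% | 2.0% | 65.3% | 49.0% |
| 5% | 5.3% | 63.3% | 47.5% |
| 10% | 11.1% | 60.0% | 45.0% |
| 15% | 17.6% | 56.7% | 42.5% |

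For comparison between strata, hold the true RR at an assumed 2, so that the correct fraction is 50.0% everywhere. The odds-ratio version is 50.0/0.98 = 51.0% at p0 = 2% and 50.0/0.90 = 55.6% at p0 = 10%.

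**4. If a population fraction is meant.** Take 13.9% exposed and an assumed RR of 2. The share of deaths with IAPI is 0.139 × 2/(0.139 × 2 + 0.861) = 0.278/1.139 = 0.2441. The correct population fraction is 0.2441 × 0.500 = 12.2%.

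- Share of deaths exposed times (1 − 1/OR): at p0 = 5%, 0.2441 × 0.5263 = 12.8%; at 10%, 0.2441 × 0.5556 = 13.6%. The gaps are 0.6 and 1.4 percentage points.
- Prevalence form, p(OR − 1)/[1 + p(OR − 1)] with p = 0.139 and OR = 2.111 or 2.250: 13.4% and 14.8%. The gaps are 1.2 and 2.6 points.
- Among the exposed, the corresponding gaps are 52.6 − 50.0 = 2.6 and 55.6 − 50.0 = 5.6 points.

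At these values the absolute gap is smaller for the population fraction under either formula.

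**The case against.** The strongest defence is that the approximation is disclosed and probably harmless. Eligibility covers surgical patients in general rather than an intensive-care or septic cohort, and the quantity that matters is the risk of death without IAPI. At p0 of 2% or less the fraction among the exposed moves by at most 1.4 points in the table (66.7% to 65.3%). Deaths are recorded, so the assumption can be checked later. This stands as a limit on size. It does not rescue the case-control premise, which is wrong at any mortality rate.

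A reader might infer more than the documents support:

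- **That the attributable fraction will be materially inflated, above all in the sickest admission types.** No mortality figure is given and admission types are undefined, so this is possible but not shown.
- **That the mortality figures in Section 2.5.2 (about 10% with a SOFA change of 2 or more in suspected infection, above 40% in septic shock) are the relevant baseline.** They describe complications, not admission types or patients without IAPI.
- **That the bias is always upward.** It is upward only if the odds ratio exceeds 1.
- **That the table gives the exact bias.** The planned odds ratio comes from a mixed model and is conditional on its random effect, whereas the conversion treats it as marginal. The plan also does not say which attributable fraction it means.

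**Conclusion.** The point holds as a contradiction in the text plus a conditional caution. Section 4.2.3 relies on a case-control design that appears nowhere else in the document and on a rarity assumption with no figure or check behind it. The cohort data make both unnecessary.

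The size depends on p0, which the document does not give. The relative overstatement among the exposed runs from about 1% at p0 = 1% to about 18% at p0 = 15%, assuming an odds ratio above 1 and reading it as marginal. If death is rare in every admission type, the numerical effect is negligible. In a high-mortality stratum it could matter, both for the fraction itself and for comparisons between strata.

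This is a desirable correction to a secondary analysis. A reader might take it as a threat to the main result, but the sample size in Section 4.1 and the prediction model in Sections 4.2.1 and 4.2.2 do not use this quantity.

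**What to change.** In Section 4.2.3:

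- Delete the sentence on the case-control design and rare death.
- From the weighted model already planned, compute standardised risks of death with and without IAPI within each admission type. Report the risk difference, risk ratio and attributable fraction from those risks, with bootstrap confidence intervals.
- Define the admission types, and state whether the fraction is among the exposed or in the population.
- Name the death endpoint. The abstract and Sections 2.5.2 and 4.2.3 use in-hospital mortality (the abstract and Section 4.2.3 refer to three months), while Section 4.2 refers to 90-day mortality. These need to be reconciled before the risks are defined.

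The cost is revised wording and a little more analysis; no new data are needed. If IAPI is associated with higher mortality, the reported fraction becomes slightly smaller. The change removes only the odds-ratio approximation. The weights in Section 4.2.3 also include surgical complications, which may follow IAPI, and standardising the risks does not settle whether that adjustment is sound.

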#### ***4.2.4 Methodological considerations***

##### ***4.2.4.1 Alternate definition of potential predictor variables case considered.***

Potential predictor variables could be inconsistent in definitions of Norton scale, Waterlow scale, Braden scale, Cubbin & Jackson scale, and Munro scale. The quartiles or dichotomous categories of predictor variables will be used as covariates for a specific patient population, while employing classification homogenization to improve clarity for the assessor. Our objective is to attain increased simplicity and validity in assessment scales.

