### **Methods:**

We will use a pre-set observational assessment scale that consists of 24 indicators to construct the predictive model in this study. In addition to these pre-set indicators, the researchers will also collect other relevant indicators that they believe may contribute to the predictive model. Primary outcome was incidence of IAPI of any stage at 7 days from operating room admission. Secondary outcomes were in-hospital mortality (follow-up endpoint is 3 months after surgical procedure), surgical complication, and hospitalization costs. The prospective cohort study dataset is divided randomly into two

subsets: a training group (80% of the data) and an internal validation group (20% of the data). The training group is used for model development, while the internal validation group remains untouched until later stages. In model development, researchers can explore different variables and test various machine learning algorithms, such as logistic regression, artificial neural network (ANN), XGBoost, support vector machine (SVM), k-nearest neighbors (k-NN), naive Bayes, gradient boosting machines (GBM), AdaBoost, Gaussian mixture model (GMM), and support vector regression (SVR). They can train and optimize these models using the training dataset. After training the models on the training dataset, researchers can evaluate their performance using appropriate evaluation metrics (e.g., accuracy, precision, recall, F1-score, area under the receiver operating characteristics curve). Based on the evaluation results, we refine the model by tweaking hyperparameters, feature selection, or employing techniques like cross-validation or grid search. This iterative process aims to find the best-performing model configuration. Once the model is optimized using the training dataset, it is then evaluated on the internal validation dataset. This evaluation serves as an unbiased assessment of the model's performance on unseen data, providing an estimate of its ability to generalize. Based on the performance on the internal validation dataset, to choose the best-performing model as the final predictive model.

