### ***2.5.3 Predictors***

Physiological observation indicators for all surgical patients were recorded as actual observed values within the first 24 hours preoperative, while other intraoperative observation indicators (such as anesthesia method, body temperature, blood pressure,

surgical time, blood loss, etc.) were documented based on actual observations during surgical procedures. Data collection was conducted independently using commonly employed scales for these observation indicators (Table 1):

Clearly define all outcomes, exposures, predictors, potential confounders, and effect modifiers. Give diagnostic criteria, if applicable

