## 4. Data Analysis

### 4.1 Sample size

The primary outcome of this study is IAPI in patients who underwent surgery procedure.

The fixed position of surgical patients in the surgical procedure, and the occurrence of IAPI risk is time-dependent, which it is positively correlated with the advancement of time and the occurrence of IAPI events in surgical patients. For time-to-event outcomes, ensure the sample size is enough to: Estimate the overall outcome proportion with sufficient precision at one or more key time-points in follow-up; Target a shrinkage factor of 0.9; Target small optimism of 0.05 in the apparent  $R^2_{\text{Nagelkerke}}$ . The formula provided by Riley et al. is as follows:

Time-event-outcome, the sample size (number of participants, n) required to achieve the expected uniform contraction coefficient S can be expressed as:

$$n = \frac{P}{(S-1)\ln\left(1 - \frac{R_{cs}^2}{S}\right)}$$

To calculate the sample size, to ensure that the expected optimistic value of  $R^2$  (i.e.,  $R_{cs}^2/\max(R_{cs}^2)$ ) has a smaller expected optimism. For time-event-outcome, the first step is to calculate the contraction coefficient corresponding to the expected optimistic value in  $R^2_{\text{Nagelkerke}}$ :

$$S = \frac{R_{cs}^2}{R_{cs}^2 + \delta\max(R_{cs}^2)}$$

The recent randomized controlled trial results showed an incidence of IAPI (stage I and above) of 13.9%, assuming 0.05 acceptable difference in apparent & adjusted

R-squared. The study used the R4.1.2 software (pmsampsize package) to estimate the minimum sample size required to develop the new model. Minimum sample size required for new model development is 4115, with 572 events (assuming an outcome prevalence = 0.139) and an Events per Predictor Parameter (EPP) is 23.83. In addition, according to the pre-model design requirements, the total sample was divided into 80% samples for the development of the new model and 20% samples for the validation of the model. This means that a total of 5144 cases are required. Considering a possible 10% loss of follow-up, the minimum sample size required for the prediction model was 5658 cases.

```
NB: Assuming 0.05 acceptable difference in apparent & adjusted R-squared
NB: Assuming 0.05 margin of error in estimation of intercept
NB: Events per Predictor Parameter (EPP) assumes prevalence = 0.139
```

	Samp_size	Shrinkage	Parameter	CS_Rsq	Max_Rsq	Nag_Rsq

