Criteria 1	4115	0.900	24	0.051	0.553	0.092
Criteria 2	833	0.648	24	0.051	0.553	0.092
Criteria 3	184	0.900	24	0.051	0.553	0.092
Final	4115	0.900	24	0.051	0.553	0.092
		EPP				
Criteria 1	23.83					
Criteria 2	4.82					
Criteria 3	1.07					
Final	23.83					

```
Minimum sample size required for new model development based on user inputs = 4115,
with 572 events (assuming an outcome prevalence = 0.139) and an EPP = 23.83
```

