After variable selection with RFE, we will be trained potential seven statistical models with centred and scaled selected predictors because of the different scales of the predictors and to ease the intercept of models to the IAPI, including a logistic regression, decision tree, random forest, artificial neural network (ANN), eXtreme Gradient Boosting algorithm (XGBoost), support vector machine (SVM), k-nearest neighbors (k-NN). Logistic regression is suitable for binary classification problems, while decision trees can handle both binary and multi-class problems. Random forests and XGBoost are based on decision trees and are known for their good performance in predicting both continuous and categorical variables. ANNs can be used for nonlinear problems, but they require more time for training. SVM and k-NN are also popular for classification problems, but they require different preprocessing techniques.

To evaluate the performance of each model, we will be using the cross-validation. With k-fold cross-validation, the data is randomly divided into k subsets, and each model is trained on k-1 subsets and tested on one subset. This process is repeated k times, with each of the k subsets being used once as the test set. The average

performance across all k tests is then used as the final performance measure. To assess the degree of potential over-fitting of each algorithm, we will be trained them using a 10-fold 10-repeat cross-validation procedure.

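### Predictor coding is inconsistent: section 4.2.4.1 uses quartile or two-group categories where 2.5.3 and 4.2.1 point to measured, scaled values; this loses information, and indicator-coded quartiles are not covered by n = 4115

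*Combined protocol and SAP*

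**What the plan says.** Four parts of the combined protocol and SAP bear on how predictors are coded.

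- **Section 4.2.4.1**, whose heading speaks of an alternate definition, starts from the fact that the five existing scales define the same items differently. It then says: "The quartiles or dichotomous categories of predictor variables will be used as covariates for a specific patient population". It does not name the variables, the cut-points, the patient population or the coding. The stated aim is a simpler and more valid assessment.
- **Section 2.5.3** says preoperative physiological indicators are "recorded as actual observed values within the first 24 hours preoperative". Intraoperative indicators, with body temperature, blood pressure, surgical time and blood loss among the examples, are documented from what is observed during surgery.
- **Section 4.2.1** trains "seven statistical models with centred and scaled selected predictors because of the different scales of the predictors". It prescribes no categorisation.
- **Section 4.1** sizes the development sample for 24 predictor parameters and reports "an Events per Predictor Parameter (EPP) is 23.83". The Methods paragraph of the abstract describes a pre-set scale of 24 indicators, so the calculation appears to allow one parameter per indicator.

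Table 1 lists nearly all candidates, including age, BMI, temperature, length of surgery and blood loss, as ordered or nominal categories.

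**The concern.** Two analysts could follow this plan and fit different models: one with blood loss as a scaled measurement, the other with blood loss in two or four groups. The choice matters in three ways.

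1. **Information.** Patients within a group are treated as identical, so part of the predictor's signal is lost. Section 4.2.2 compares the new models with five established scales, using AUC to assess discrimination, so any loss falls on the main comparison.
2. **Transfer.** Quartiles or medians taken from the sample depend on who was recruited. A bedside score needs thresholds that stay the same elsewhere.
3. **Sample size.** A predictor in quartiles, coded with indicator terms, costs three parameters instead of one. Section 4.1 makes no allowance for this.

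Nor does the stated aim require categories at the fitting stage. Table 1 bands age in three different ways (Waterlow, Cubbin & Jackson, Munro). Measured age would remove that inconsistency, whereas sample quartiles would add a fourth banding. Section 4.2.4.2 already derives a points system from a fitted logistic model, so simplification can follow fitting.

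**Working it through.** **Inputs (section 4.1).** Parameters P = 24; Cox-Snell R² = 0.051; target shrinkage S = 0.90; prevalence 0.139. The output row reads "Criteria 1 4115 0.900 24 0.051 0.553 0.092".

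**Step 1: reproduce the plan's figure.** The printed formula is n = P / [(S − 1) ln(1 − R²/S)].

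- 1 − 0.051/0.90 = 0.94333, and its natural log is −0.058336.
- (−0.10) × (−0.058336) = 0.0058336.
- n = 24 / 0.0058336 = 4114.1, rounded up to 4115.
- Events: 4115 × 0.139 = 572. EPP: 572/24 = 23.83.

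All agree with the plan.

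**Step 2: parameter count under quartiles.** Four groups with indicator coding need three terms in place of one linear term, an addition of two. With k numeric predictors so coded, P = 24 + 2k. At fixed S and R², n is proportional to P.

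**Step 3: consequences.** Two quantities follow for each k: the n that restores S = 0.90, and the S obtained by solving the same formula at n = 4115 with R² held at 0.051.

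| k quartiled | P | n for S = 0.90 | S at n = 4115 | EPP at n = 4115 |
|---|---|---|---|---|
| 0 | 24 | 4115 | 0.90 | 23.8 |
| 4 | 32 | 5,486 | 0.87 | 17.9 |
| 8 | 40 | 6,857 | 0.84 | 14.3 |
| 24 (upper bound) | 72 | 12,343 | 0.75 | 7.9 |

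Example for k = 4: 4114.1 × 32/24 = 5485.5, rounded up to 5,486; EPP = 572/32 = 17.9. Check on S: with S = 0.871, 32 / [(−0.129) × ln(1 − 0.051/0.871)] is about 4,111, close to 4115.

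The choice k = 4 corresponds to the four numeric intraoperative examples in section 2.5.3. The choice k = 8 is an assumption: the Table 1 items with a natural numeric form, namely age, BMI or weight, weight loss, fasting time, temperature, blood-pressure change, length of surgery and blood loss. The documents do not give k.

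**Step 4: cases with no added parameters.** A dichotomy uses one parameter. So does a four-level variable entered as one ordinal score. Either leaves P = 24 and n = 4115.

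**Step 5: information kept.** For a standard normal predictor with a linear effect, the share kept is the between-group variance.

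- Median split: 2/π = 0.637.
- Quartiles: the group means are ±1.271 and ±0.325, so the share is 0.5 × 1.271² + 0.5 × 0.325² = 0.861.

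**The case against.** The strongest reply is that section 4.2.4.1 is not the primary modelling plan. It sits under a heading about alternate definitions, is confined to an unspecified patient population, and addresses inconsistent item definitions. Many Table 1 items already have four levels, so quartiles might even mean harmonised four-level items, not sample quartiles. Section 4.2.1 asks for no categorisation, and an ordinal score can be centred and scaled as one term, which leaves the parameter count unchanged. Collapsing could even save parameters: indicator-coded as listed, Waterlow age has five levels and skin type seven.

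Much of this stands, and it limits what can be claimed. A reader might infer three stronger things that the documents do not support:

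- **That every predictor will be cut before modelling.** The scope of the sentence is unclear, and it conflicts with the natural reading of section 4.2.1.
- **That the parameters behind n = 4115 triple.** This needs all 24 to be numeric, quartiled and indicator-coded. Most Table 1 items are already categorical.
- **That raw age and BMI are recorded.** Section 2.5.3 names neither, and Table 1 shows both only in bands.

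The reply does not remove the inconsistency. The sentence says the categories will be used, and nothing in the plan says when, for which variables or with what coding. The information loss applies to any measured predictor that is cut, including by dichotomy, where no parameters are added.

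The gap between 24 parameters and the 51 items of Table 1 is a separate question that exists whatever is decided about quartiles. It is not counted here.

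**Conclusion.** The point holds as a conflict over predictor coding that must be reconciled, with a better method available at little cost. It does not hold as a claim that the plan's parameter count has tripled.

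- **Information.** A measured predictor that is cut keeps about 64% (median split) or 86% (quartiles) of its information. This assumes normality, a linear effect and cuts at the median or quartiles. A skewed variable such as blood loss may behave differently, and the documents give no basis for putting a figure on the AUC loss.
- **Sample size.** If quartiles are entered with indicator terms, the plan misses its own 0.90 target at n = 4115. Over k = 4 to 8, shrinkage is about 0.87 to 0.84 and the required development sample about 5,486 to 6,857. The figures 0.75 and 12,343 are an upper bound. They assume one parameter per indicator in the stated 24 and an unchanged R² of 0.051.
- **No sample-size effect** arises from dichotomies or single ordinal terms.

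**What to change.** Amend section 4.2.4.1, and align sections 2.5.3 and 4.2.1 with it, as follows.

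1. Predictors captured as measured values enter model development as continuous terms, linear by default. These are body temperature, blood pressure, surgical time and blood loss, plus age and BMI if raw values are stored. This keeps P at 24.
2. Fixed, pre-stated bands are applied only when the final model is converted to the points score of section 4.2.4.2.
3. The AUC is reported before and after that conversion, so that the price of simplicity is visible.
4. If any predictor is still to be categorised during fitting, name it with its cut-points, coding and the population concerned, and restate P and the sample size in section 4.1.

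**Cost.** Where measured values are already stored, this is a change of SAP wording. Where the form captures only bands, raw values would have to be entered, which means changing the data form. Any spline adds one or two parameters per variable, so splines should be limited to a few pre-named predictors and counted in P.
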